10.2 Manufacturing, packaging and labelling

The IMP, including placebo, is manufactured by Recipharm Pharmaceutical Development AB, Solna, Sweden, and Recipharm Pessac, Pessac, France.

Primary packaging and release will be performed by Recipharm Pessac, France, and labelling and secondary packaging will be performed by Recipharm, Solna, Sweden. Primary individually packed IMP contains 42 capsules per bottle. The bottle and closure are compliant to food grade requirements. The bottles for the run-in phase and bottles for final dose will be packed in one plastic bag or box per individual patient. Details will be specified in a separate Pharmacy Manual. The individually packed IMP will be labelled with randomisation number and shipped to the research clinic.

Labels will comply with applicable Good Manufacturing Practice (GMP), with Annex 13 of the European Union Good Manufacturing Practice regulations and local regulatory requirements [38].

10.3 Conditions for storage

Both EMP16-02 60/20 and EMP16-02 90/30 capsules should be stored in the fridge (2°C to 8°C) to prolong stability to up to 12 months. Single capsules can be stored at room temperature for a maximum of 12 h.

At temperatures above 40°C, the G3 fraction containing or listat can melt, which may affect the granulation of the fraction and as such the release of or listat and the efficacy of the IMP. This may result in gastrointestinal symptoms. No toxic degradation products have been observed in stability tests.

10.4 **Preparation and accountability**

Each site and the Investigator will maintain a Storage and Accountability Log as well as a Drug Dispensing Log detailing the dates and quantities of study medication received and used by each patient, and study medication destroyed at the safety follow-up visit (Visit 6). Any discrepancies between prepared and returned IMP must be explained and documented. Products deliberately and/or accidentally destroyed by the site or the patient must be accounted for.

CONFIDENTIAL 54 (92)

10.5 **Treatment administration**

The patients will be treated with IMP for a period of 26 weeks.

At the clinic, the IMP will be dispensed by site staff, *e.g.*, a study nurse, directly from the individually packed boxes. At home, the patients will self-administer the IMP. The IMP should be taken halfway into a meal, with approximately 100-200 mL water or other drink. The patient should be instructed to not take more than 200 mL water or other drink during the meal, as this can affect the efficacy of the IMP.

The IMP should preferably be taken halfway through each of the three main meals during the day, but can be taken up to 1 hour after the meal. If a dose of EMP16-02 is missed more than 1 hour from the start of the meal, the dose should not be taken. The IMP should not be taken on an empty stomach. If the patient is not eating three main meals on a day, the IMP can be taken with a lighter snack as well. The patients will be recommended to leave 3-4 h between each meal/IMP dose.

The first IMP dose will be taken at home in association with lunch (or other main meal following breakfast) on Day 1 (after Visit 2). One placebo capsule will be given to all patients in association with breakfast at the clinic on Day 1 (Visit 2).

The last dose will be taken at the clinic in association with breakfast on Day 179±3 days (Visit 5, week 26; in total one dose on Day 179).

At Visit 3 and Visit 4 IMP will be taken at the clinic in association with breakfast. All other doses will be taken at home.

IMP will be handed out to the patients at Visit 2 (for week 1-8), Visit 3 (for week 9-14) and Visit 4 (for week 15-26).

10.6 Continuation of treatment with Investigational Medicinal Product

There will be no treatment with EMP16-02 after Visit 5.

10.7 Treatment compliance

The compliance will be calculated by counting the number of capsules, as follows:

$$compliance = \frac{number\ of\ delivered\ capsules - number\ of\ returned\ capsules}{number\ of\ delivered\ capsules}$$

Based on timing of Visit 5, the total length of the treatment period may vary per patient. Compliance calculations should be based on the individual treatment period. IMP administration is planned as follows:

- Day 1: 2 doses of IMP (and one dose of placebo in association with breakfast)
- Day 2 to Day 178 ± 3 : 3 doses
- Day 179 ± 3 : 1 dose

CONFIDENTIAL 55 (92)

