- Compliance after 7, 14 and 26 weeks of treatment with EMP16-02 (120 mg O/40 mg A and 150 mg O/50 mg A) as compared to placebo.

Exploratory endpoints:

- The absolute difference in fasting plasma/serum levels of ApoA1 and ApoB from baseline after 7, 14 and 26 weeks of treatment with EMP16-02 (120 mg O/40 mg A and 150 mg O/50 mg A) as compared to placebo.
- Pre-dose plasma concentrations of orlistat and acarbose after 26 weeks of treatment with EMP16-02 (120 mg O/40 mg A and 150 mg O/50 mg A).
- Relative (%) and absolute change in body weight from baseline, and from end of treatment at 26 weeks, to 6 months after end of treatment with EMP16-02 (120 mg O/ 40 mg A and 150 mg O/50 mg A) as compared to placebo.
- Relative (%) and absolute change in HbA1c from baseline, and from end of treatment at 26 weeks, to 6 months after end of treatment with EMP16-02 (120 mg O/ 40 mg A and 150 mg O/50 mg A) as compared to placebo.
- Relative (%) and absolute change in blood pressure from baseline, and from end of treatment at 26 weeks, to 6 months after end of treatment with EMP16-02 (120 mg O/ 40 mg A and 150 mg O/50 mg A) as compared to placebo.

CONFIDENTIAL 5 (92)

Clinical Study Protocol EP-002 Final version v3.0 12NOV2020

The exploratory analyses may not be reported in the clinical study report (CSR). 6-month data will be reported in an addendum to the CSR.

Number of patients planned

A total of 156 patients will be randomised in the study. Assuming a dropout rate of 20%, a total of 52 patients will be randomised to each treatment arm to achieve at least 41 evaluable patients per arm.

An evaluable patient in the main part is defined as a patient who has completed 26 weeks of treatment with investigational medicinal product (IMP). An evaluable patient in the follow-up part is defined as a patient who has completed 26 weeks of treatment with IMP and the 6 months follow-up visit.

Diagnosis and main eligibility criteria

- Male and female patients with overweight or obesity, defined as BMI \geq 30, or \geq 28 kg/m² in the presence of other risk factors (*e.g.*, hypertension, glucose dysregulation such as impaired glucose tolerance and type 2 diabetes mellitus (T2DM), and/or dyslipidaemia).
- Aged ≥ 18 and ≤ 75 years.
- Willing and able to give written informed consent for participation in the study.
- Body weight stable (<5% reported change during the three months preceding screening and randomisation).

Methodology

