EMP16-02 120 mg O/40 mg A	60 mg O/20 mg A	90 mg O/30 mg A	120 mg O/40 mg A	120 mg O/40 mg A
EMP16-02 150 mg O/50 mg A	60 mg O/20 mg A	90 mg O/30 mg A	120 mg O/40 mg A	150 mg O/50 mg A

CONFIDENTIAL 34 (92)

EMP16-02 is formulated in capsules available in two strengths:

- EMP16-02-90/30, containing 90 mg O/30 mg A
- EMP16-02-60/20, containing 60 mg O/20 mg A

Placebo treatment consists of matching, oral capsules. Placebo and EMP16-02 capsules need to be taken TID together with the three main daily meals according to the schedule displayed in Table 8.1-2.

Target dose	Week 1 and 2	Week 3 and 4	Week 5 and 6	Week 7 to 26
EMP16-02 120 mg O/40 mg A	1x EMP16-02- 60/20	1x EMP16-02- 90/30	2x EMP16-02- 60/20	2x EMP16-02- 60/20
EMP16-02 150 mg O/50 mg A	1x EMP16-02- 60/20	1x EMP16-02- 90/30	2x EMP16-02- 60/20	1x EMP16-02- 60/20 1x EMP16-02- 90/30
Placebo	1x placebo capsule	1x placebo capsule	2x placebo capsule	2x placebo capsule

Table 8.1-2 Number and type of capsules to be taken

During the run-in phase, after 2, 4, (6) and 8 weeks, patients will fill in the GSRS questionnaire using the electronic diary.

Patients will come to the clinic at Visit 3 (week 7), Visit 4 (week 14) and Visit 5 (week 26) for safety assessments and assessments of weight and anthropometric measurements, as outlined in Table 8.1-3 and detailed in Table 8.1-4. Patients will arrive in the morning after at least 8 hours overnight fasting. All visits will start with a brief physical examination followed by blood sampling (fasting) and assessment of body weight and body composition. A standardised breakfast will be served during which the patient will take the IMP. All or a selection of the questionnaires, including the satiety and craving questionnaire, will be filled in in a similar way as during Visit 2, see Table 11.5-2 scheduling of the questionnaires.

After 18 and 22 weeks of treatment (Day 123 ± 3 days and Day 151 ± 3 days respectively), patients will be asked to answer questions about IMP compliance, occurrence of AEs and use of concomitant medication using an electronic diary.

New IMP will be handed out to the patients at Visit 2, 3 and 4.

At Visit 5 (week 26), the patients will take the last dose during breakfast. Visit 6 is a safety follow-up visit. Visit 7 is a 6 month follow-up visit for consenting patients who has completed the 26-week treatment period with active EMP16-02 treatment (120 mg O/ 40 mg A and 150 mg O/50 mg A) or placebo.

Efficacy assessments include:

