17.4.4 Treatment compliance

Compliance will be calculated by counting tablets, as follows:

$$compliance = \frac{number\ of\ delivered\ capsules - number\ of\ returned\ capsules}{number\ of\ delivered\ capsules}$$

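### The compliance formula divides by capsules delivered, not capsules due, so its week-7 value does not measure intake and conflicts with the individual-period sentence in Section 10.7

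*Protocol*

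**What the plan says.** Section 10.7 introduces its formula with "The compliance will be calculated by counting the number of capsules, as follows" and prints (delivered − returned)/delivered. It then notes that treatment length varies with the timing of Visit 5, adds "Compliance calculations should be based on the individual treatment period", and lists the planned doses: two on Day 1, three a day after that, and one on the last day.

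Section 17.4.4, in the statistics chapter, opens with "Compliance will be calculated by counting tablets, as follows" (the product is a capsule) and prints the same formula. It omits both the individual-period sentence and the dose plan.

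On supply, Section 10.5 states: "IMP will be handed out to the patients at Visit 2 (for week 1-8), Visit 3 (for week 9-14) and Visit 4 (for week 15-26"). Table 8.1-3 places Visit 3 on Day 46, Visit 4 on Day 95 and Visit 5 on Day 179, each ±3 days, and schedules IMP compliance at those three visits. The synopsis and Table 7.4-1 list "Compliance after 7, 14 and 26 weeks of treatment", compared with placebo, as a secondary endpoint measured by capsule count.

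**The concern.** Dividing by capsules delivered measures adherence only when the amount handed out equals the amount due by the count date. The protocol's own schedule breaks that condition at Visit 3: the patient holds eight weeks of supply but is counted in week 7. Capsules not yet due then either count as missed doses or, if the patient keeps them and they are not recorded as returned, count as taken.

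The individual-period sentence suggests that a due-based denominator was intended, but the printed equation has no place for one. A reader of 10.7 and a reader of 17.4.4 could derive different values for the same secondary endpoint. Section 6.1.2 says tolerability problems severely hamper compliance with conventional orlistat, so intake while on treatment is worth measuring cleanly here.

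**Working it through.** The protocol states no numerical compliance figure, so there is none to reproduce. The check applies the printed formula to a patient who misses no dose.

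**Inputs from the protocol**
- Capsules per dose (Table 8.1-2): 1 in weeks 1-4 and 2 from week 5, in every arm (placebo row: "1x placebo capsule", then "2x placebo capsule").
- Doses (10.7): 2 on Day 1, 3 a day afterwards, 1 on the last day.
- Supply periods (10.5): weeks 1-8, 9-14 and 15-26.
- Bottle size (10.2): 42 capsules.

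**Assumptions, not stated in the protocol**
- Exact supply with no overage (10.2 leaves pack details to a Pharmacy Manual).
- All unused capsules count as returned.
- Counts at Visits 4 and 5 are cumulative.
- The count is taken before the clinic breakfast dose at Visits 3 and 4, and after the last dose at Visit 5.

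**Delivered**
- Visit 2: 14×3×1 + 14×3×1 + 28×3×2 = 42 + 42 + 168 = 252 (six full bottles).
- Visit 3: 42×3×2 = 252. Cumulative 504.
- Visit 4: 84×3×2 = 504. Cumulative 1008.

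**Due, Visit 3 on Day 46**
- Day 1: 2. Days 2-28: 27×3 = 81. Days 29-45: 17×6 = 102. Total 185.

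**Score with perfect intake**

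| Count | Nominal day | Visit window |
|---|---|---|
| Visit 3 | 185/252 = 73.4% | 167/252 = 66.3% (Day 43) to 203/252 = 80.6% (Day 49) |
| Visit 4 | 479/504 = 95.0% | 461/504 = 91.5% to 497/504 = 98.6% |
| Visit 5 | 985/1008 = 97.7% | 967/1008 = 95.9% to 1003/1008 = 99.5% |

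**Sensitivity to the assumptions**
- Counting the clinic breakfast dose at Visit 3: 187/252 = 74.2%.
- One extra 42-capsule bottle at Visit 2, for illustration: 185/294 = 62.9%. Any overage lowers the score.
- Retained capsules not counted as returned: (252 − 0)/252 = 100%, whatever was taken.
- Visit 4 scored on the Visit 3 supply alone, with the first supply used up first: (479 − 251)/252 = 228/252 = 90.5%, where 251 is the number due to Day 56.

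**Early stoppers with perfect intake, if their final count is scored**
- Stop after Day 20: 59/252 = 23.4%.
- Stop after Day 59: 83 + 31×6 = 269; 269/504 = 53.4%.

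**With capsules due as denominator**
- Perfect intake scores 185/185, 479/479 and 985/985, all 100%. Stopping after Day 20 gives 59/59 = 100%.
- A patient taking 80% of doses to Visit 3 (0.8×185 = 148 capsules) scores 148/185 = 80%. The printed formula gives 148/252 = 58.7%, which is below the perfect-intake value at every day of the visit window but cannot be read as 80%.

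**The case against.** The strongest reply is that 73% is not simply what the formula gives. Visit 3 hands out stock for weeks 9-14, so a patient seen on Day 46 still needs the remaining capsules for weeks 7-8, and nothing says they are returned. This stands: 73.4% is conditional. It does not rescue the formula, because the alternative reading yields 100% regardless of intake.

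A second reply is that 10.7 already contains the remedy, with the individual-period sentence and the dose list, and that derivations belong in the SAP. The sentence does point to the right denominator. But the protocol fixes the equation itself, twice, without using it, and the sentence is motivated only by variation in Visit 5 timing.

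A reader might infer that arms with more early stoppers will look less compliant. The documents do not establish this. Compliance is scheduled only at Visits 3, 4 and 5. A withdrawing patient is asked to undergo Visit 6 procedures, which carry no compliance row. Section 9.8.3 requires final drug accountability but does not say that it becomes an endpoint value. Section 17.1 rules out imputation. The effect therefore needs both that those counts are scored and that stopping differs by arm. Capsule numbers are equal across arms, so the Visit 3 shortfall alone shifts all arms alike.

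A reader might also want every unreturned bottle treated as missing. That is a preference: Section 10.4 already requires discrepancies between prepared and returned product to be explained and documented.

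**Conclusion.** The point holds for the formula and for week 7. As printed, the week-7 value of a secondary endpoint is not a valid measure of intake. With an exact 252-capsule supply and all unused capsules counted as returned, perfect intake scores 73.4%, and the visit window alone moves it between 66.3% and 80.6%. If retained capsules are not counted as returned, everyone who hands nothing back scores 100%. The formula and the individual-period sentence in 10.7 contradict each other, and 17.4.4 carries only the formula.

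It would be too strong to say that the endpoint reflects visit timing and drop-out rather than intake throughout. On cumulative counts, perfect completers lose about 5 points at week 14 and 2 at week 26. Bias between arms is possible but conditional on unequal early stopping. The primary analysis is untouched, and no numerical compliance threshold governs withdrawal or the per protocol set. This is a correction worth making, not a threat to the main conclusion.

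**What to change.** In both 10.7 and 17.4.4, define compliance as (capsules dispensed − capsules remaining at the count, whether returned or retained) / (capsules due from first dose to the count date, or to last dose if earlier). Take capsules due from Table 8.1-2 and the dose plan in 10.7. Say whether the values at weeks 14 and 26 are cumulative or per interval, and whether the clinic breakfast dose is included on both sides of the ratio. State whether the final accountability of early stoppers enters the endpoint. Replace tablets with capsules in 17.4.4.

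The cost is a small derivation change, plus recording at Visit 3 the number of capsules the patient still holds.

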10.8 Return and destruction of investigational medicinal products

Any unused study medication will be destructed at each site following confirmation by the Sponsor. Empty containers will be destroyed at the study sites. The Monitor will perform final IMP accountability reconciliation at the study end to verify that all unused IMP is adequately destroyed and documented.

11 STUDY ASSESSMENTS

The study assessments are described in the sections below and the timing of these assessments are detailed in the overall schedule of events (Table 8.1-3) and in the detailed schedule of events for Visit 2 to 5 (Table 8.1-4).

11.1 Recording of data

The Principal Investigator will provide the Sponsor with all data produced during the study from the scheduled study assessments. He/she ensures the accuracy, completeness, legibility, and timeliness of the data reported to Sponsor in the eCRF and in all required reports.

11.2 Electronic diary

An electronic diary (ViedocMeTM) will be used to collect the following information:

- Questionnaires at visits outlined in Table 11.5-2:
 - o Meal pattern, see Section 11.5.4.1.
 - o Gastrointestinal tolerability (GSRS), see Section 11.5.4.2.
 - o Satiety and craving, see Section 11.5.4.3.
 - o Activity and sleep, see Section 11.5.4.4.
 - o Health and quality of life RAND-36, see Section 11.5.4.5.
- IMP compliance, AEs and concomitant medication (at week 18 and 22, i.e. between Visit 4 and Visit 5).

11.3 Demographics and other baseline characteristics

11.3.1 Informed consent

Signed informed consent must be obtained before any screening procedures in the main part of the study are initiated. A separate informed consent must be obtained before the 6 months

CONFIDENTIAL 56 (92)

Clinical Study Protocol EP-002 Final version v3.0 12NOV2020

follow-up part (Visit 7) is initiated. The informed consent procedure is further described in Section 14.3.

11.3.2 Eligibility criteria

Eligibility criteria should be checked during screening and verified before randomisation/IMP administration. The criteria are specified in Sections 9.4 and 9.5.

11.3.3 Demographic information

The following demographic data will be recorded: gender, age, ethnicity and race.

11.3.4 Medical history and obesity history

Medical and obesity history will be obtained by patient interview in order to verify that the eligibility criteria are met.

The medical history should include all relevant diseases and operations as judged by the Investigator.

11.3.5 Prior and concomitant medication

Prior medications taken within two weeks will be obtained by patient interview in order to verify that the eligibility criteria are met (see also Section 9.6.2).

Medications are classified as prior if the stop date was before or on the day of the first dose administration (pre-dose) and as concomitant if ongoing on the day of the first dose administration, stopped after the first dose administration or started after the first dose administration. To distinguish between prior and concomitant medications on Day 1 (*i.e.*, the first dosing day), the start time of any newly introduced medication or the stop time of any previously ongoing medication must be recorded in the eCRF.

Any use of concomitant medication from screening until the safety follow-up visit (Visit 6) must be documented appropriately in the patient's eCRF. Relevant information (*i.e.* name of medication, dose, unit, frequency, dose form, route of administration, start and stop dates, reason for use) must be recorded. All changes in medication should be noted in the eCRF.

11.3.6 HIV and Hepatitis B/C

Patients will be tested for HIV and hepatitis B/C prior to inclusion into the study. Any positive result will exclude the patient from participating in the study.

11.3.7 Alcohol breath test

An alcohol breath test will be performed at all visits to the clinic (Table 8.1-3).

11.3.8 Pregnancy test

All WOCBP will do a pregnancy test (urine dipstick) at all visits to the clinic (Table 8.1-3).

CONFIDENTIAL 57 (92)

11.3.9 Urine drug screen

Urine will be screened for drugs of abuse at time points outlined in the schedule of events (Table 8.1-3) using the AlereTM Drug Screen Test Panel. Additional random tests can be performed during the study period.

11.3.10 Baseline symptoms

A baseline symptom is defined as an event that occurs between the patient's signing of the ICF until the first administration of IMP (i.e. an event that occurs during the screening period). Such events are not AEs and will be recorded as baseline symptoms in the Medical History Log in the eCRF.

11.4 Assessments related to primary endpoints

11.4.1 Weight

Weight will be measured in kg (one decimal) without shoes and without thick clothes such as jumpers at visits specified in Table 8.1-3.

Weight at Visit 2 will be compared with weight at Visit 1 prior to randomisation, to ensure that the patient is fulfilling inclusion criterion #6.

All patients completing the treatment period in the main part of the study will be asked to participate in the follow-up part where weight will be measured 6 months after end of treatment (Visit 7). Weight at Visit 7 will be compared with the weight at Visit 2 (baseline) and the weight at Visit 5 (end of 26-weeks treatment).

11.5 Assessments related to secondary endpoints – efficacy

11.5.1 Anthropometric measurements

11.5.1.1 Height and BMI

Height will be measured in cm (no decimals) without shoes at visits specified in Table 8.1-3. BMI will be calculated with height measured at Visit 1 for all timepoints where BMI is assessed (Section 11.4.1).

11.5.1.2 Waist circumference

Waist circumference will be measured in cm (one decimal) at visits specified in Table 8.1-3.

11.5.1.3 Sagittal diameter

Sagittal diameter will be measured in cm (one decimal) at visits specified in Table 8.1-3.

For measurement of the sagittal diameter, the patient will need to lie down on his/her back while having knees bent, so that even the lower back is in contact with the surface he/she is

CONFIDENTIAL 58 (92)

lying on. The distance from the back to the highest point of the abdomen will be measured in cm while the patient exhales.

11.5.1.4 Bio-impedance

Body composition (% body fat) will be measured using a bio-impedance measuring device, according to the manufacturer's instructions, at visits specified in Table 8.1-3.

11.5.2 Lipid metabolism, glucose metabolism and inflammation markers

Venous blood samples (4 mL) will be collected to analyse the fasting profile of lipid metabolism markers, glucose metabolism markers, and inflammation markers, as detailed in Table 11.5-1. All parameters will be analysed in immediate association with sampling.

If indicated, total cholesterol, LDL, HDL and triglycerides can be measured at screening to verify if the patient fulfils inclusion criterion #3.

Timing of the assessments is outlined in the overall schedule of events (Table 8.1-3) and in the detailed schedule of events for Visit 2 to 5 (Table 8.1-4).

Table 11.5-1	Glucose metabolism,	lipid metabolism and	l inflammation markers

Patient state	Parameter
Fasting	Hb1Ac
· ·	Total cholesterol
	LDL
	HDL
	Hs-CRP
	Albumin
	Glucose
	Insulin
	Triglycerides

